Since their approval by the Food and Drug Administration in 2011, non-ablative, fractional laser treatment has emerged as a viable therapeutic modality for facial rejuvenation in patients with skin of color, using low-energy, low-density settings to reduce the risk of iatrogenic dyspigmentation. Recently, non-ablative fractional lasers of 1927 nanometers have been used successfully in patients with skin of color to treat acne scarring, facial hyperpigmentation and melasma [7-10]. For individuals with skin of color, adjunctive regimens have emerged to minimize the risk of iatrogenic, postprocedural hyperpigmentation. Popular adjuncts include prescribing several weeks of retinol, 2-4% hydroquinone, and/or corticosteroids, up to 1 month preceding the study and following treatment, and epidermal cooling or topical corticosteroid post-treatment to minimize heat exposure and inflammation. The literature suggests routine and varied use of these topical regimens in this population in both clinical research and clinical practice [11].

While some trials have leveraged fractionated, non-ablative 1927nm for the treatment of dyschromia or acne scarring among SPT I-V, to our knowledge, there is a paucity of studies that quantify hyperpigmentation or melasma response among patients with Fitzpatrick Skin Prototype VI. In this study, we sought to quantify efficacy of this laser in a population comprised of patients of Fitzpatrick Skin Phototypes V and VI.

Purpose and Objective

This single-center observational study is being conducted over the course of 7-12 months.

Part 1 will consist of one Initial Screening Visit (-42 to -28 Days) and use of the topical regimen will be started for at least 30 days before the treatment series are scheduled. Following the subjects consistent use of topical medications three treatments (Day 0, Day 30, Day 60) will be scheduled followed by 1-month and 3-month follow-up visits (Day 90 and Day 150).

Part 2 will consist of a Screening Visit followed by a 30-day washout period of any prescription grade topical regimen on the face. Following the washout period subjects will be scheduled for three 1927 treatments (Day 0, Day 30 and Day 60). After each treatment subjects will be asked to apply Clobetasol twice a day for four days and apply ice to the treated area four times a day. Subjects will return to for follow up visits at 1-month and 3-month (Day 90 and Day 150).

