Healthy subjects within the study population of interest who will be undergoing fractionated 1927nm laser to treat hyperpigmentation will be recruited for the study through IRB-approved recruitment flyers, emails, and social media posts. Potential subjects will be screened to check if they are acceptable candidates by a designated member of the research team. Additionally, if subjects inquire about the study during an unrelated clinic appointment with [name], or staff aesthetician, he or she may discuss the study with the potential subject and assess the treatment area.

If a subject is deemed an eligible candidate, [name] will connect the patient with a research coordinator, investigator, or designated member of the research team to answer further questions. Subjects meeting all eligibility requirements will be scheduled for an official screening visit. Candidate subjects will have the study explained to them, will be asked about their willingness to participate in the study, and their willingness to sign an informed consent form.

Informed Consent Form

An IRB-approved informed consent form (ICF) explaining the purpose, design, risks, benefits, and timeline of the study will be given to each candidate subject prior to participation in any study procedures. The candidate subject will be given as much time as needed to read the ICF and will have the opportunity to ask study-related questions and have them answered by a member of the research team. Each participating subject's signed ICF will be retained in the study file and each subject will receive their own signed copy. By signing the consent form, subjects indicate and confirm that they are willing to have their full-face photographed and acknowledge that these photos may be used for scientific publication. If the subjects decline permission to be photographed, they may not participate in the study as photographs will be used to both qualitatively and quantitatively assess the treatment outcome and are a critical tool for study evaluation. The candidate subject will be ineligible to participate in this study without a signed ICF.

Subject Identification

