Subjects will be assigned a 2-digit Subject Number, which, when used in conjunction with the Clinical Study ID, will uniquely identify each subject participating in the study. The Subject Number will remain unchanged throughout the study and should be used in all references to the individual in this study. No number will be reassigned once the study begins.

Eligibility Criteria

Inclusion Criteria: Part 1 & Part 2

1. Healthy male, female, and non-binary adults between 18 and 75 years of age
2. Fitzpatrick Skin Phototype V and VI
3. Individuals undergoing fractionated 1927nm laser to treat hyperpigmentation in the past 3 months.
4. Individuals willing to withhold aesthetic therapies (excluding those explicitly prescribed by the Investigator as pre-treatment) for the duration of the study
5. Women of childbearing potential who agree to take a urine pregnancy test at the Screening visit or when deemed by Investigator. Women of childbearing potential must have a negative urine pregnancy test and must not be lactating at Screening. Women must be willing and able to use an acceptable method of birth control (see below) during the study. Women will not be considered of childbearing potential if one or more of the following is documented:
 - Postmenopausal for ≥ 12 months prior to initiation of the study
 - Without a uterus +/- both ovaries prior to initiation of the study
 - Bilateral tubal ligation ≥ 6 months prior to initiation of the study
6. Individuals of childbearing potential who use an acceptable method of contraception for the duration of the study. Acceptable modes of birth control include the following:
 - Established use of hormonal contraception (oral, injectable, implanted, patch or vaginal ring)
 - Barrier methods with spermicide: condom or occlusive cap (diaphragm or cervical/vault caps) with spermicidal foam/film/cream/suppository
 - Intrauterine device (IUD) or intrauterine system (IUS)
 - Surgical sterilization (e.g., vasectomy confirmed to be effective by sperm count check, tubal occlusion, hysterectomy, bilateral salpingectomy/oophorectomy)
 - Abstinence from heterosexual intercourse, when this is in line with the preferred and usual lifestyle of the subject. Periodic abstinence (e.g., calendar, ovulation, symptothermal, post-ovulation methods) and withdrawal methods are not acceptable forms of contraception.
7. Individuals who can read, speak, write, and understand English and who are willing to provide written informed consent.

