Visit 1 Day -42 to -28	Visit 2 Day 0	Visit 3 Day 30 (± 3 days)	Visit 4 Day 60 (± 3 days)	Visit 5 Day 90 (± 7 days)	Visit 6ay 150 Day 150 (± 7 days)	Visit 7 Day -30 to -1	Visit 8 Day 0	Visit 9 Day 30 (± 3 days)	Visit 10 Day 60 (± 3 days)	Visit 11 Day 90 (± 7 days)	Visit 12 Day 150 (± 7 days)		
R	Eligibility Criteria & Informed Consent	●											
R	Enrollment Paperwork	●											
R S	Medical History & Concomitant Medications	●	●	●	●	●	●	●	●	●	●		
S	Pregnancy Test	●											
S	Tretinoin/ 4% Hydroquinone	●	●			●							
S	MOXI Treatment		●	●	●								
S	Clobetasol /Ice	████████	████████	████████	████████	████████	████████	████████	████████	████████	████████		
S	Standard Photography	●				●	●					●	●
R	Vectra H2 3D Photography	●				●	●					●	●
R	VISIA-CR Photography & Skin Imaging Analysis	●				●	●					●	●
R	Safety Assessment	●	●	●	●	●	●	●	●	●	●	●	●

Wash out Period (4-6 weeks)

R= Research procedure; S=Standard of Care procedure and/or VISIA-CR

Pre-Study Procedures

Prior to the start of the study, potential subjects will be screened for eligibility requirements via chart review on EPIC. Prospective subjects will be informed of study details and study visit instructions as detailed in section 6. An appointment to visit the clinic for an official screening visit will be scheduled if interest is demonstrated. Additionally, if subjects express an interest in the procedure during a clinic appointment with [name], he may discuss the study with them and assess the treatment area. If a subject is deemed a good candidate, they will be connected to a research coordinator to answer any further questions and provide consent.

Part 1

Visit 1: Screening Visit

Day -42 to -28 Days

The purpose of the study, eligibility criteria, and potential risks will be discussed with the potential subject. All interested candidates will be given an IRB-approved Informed Consent Form (ICF) as detailed in this protocol, with adequate time for review. The Investigator and/or designee will address questions and/or concerns raised by the subject. Those subjects who elect to participate will sign the consent form prior to any study procedures. The subject will receive a signed copy of their ICF and the original will be kept in the study file. Subjects will then be screened to ensure they meet all study criteria.

The following is a complete list of the screening and enrollment activities to be performed:

1. Obtain informed consent and HIPAA authorization.

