5. Obtain post-treatment photographs using the Vectra H2 3D Imaging System, as described in section entitled, "Assessments", for research purposes
6. Obtain post-treatment photographs VISIA and/or VISIA-CR as described in section entitled, "Assessments", for research purposes.

These visits will take about 30 minutes.

Part 2

Visit 1: Screening Visit

Day -42 to -28 Days

The purpose of the study, eligibility criteria, and potential risks will be discussed with the potential subject. All interested candidates will be given an IRB-approved Informed Consent Form (ICF) as detailed in this protocol, with adequate time for review. The Investigator and/or designee will address questions and/or concerns raised by the subject. Those subjects who elect to participate will sign the consent form prior to any study procedures. The subject will receive a

signed copy of their ICF and the original will be kept in the study file. Subjects will then be screened to ensure they meet all study criteria.

The following is a complete list of the screening and enrollment activities to be performed:

8. Obtain informed consent and HIPAA authorization.
9. Assign a screening number to candidate subjects that sign the initial paperwork. If subject is continuing the study from Part 1 they will use the same screening number assigned.
10. If not already collected, collect a brief medical history including current medications, skin type, allergies, major conditions, or illnesses, etc. and assess if subjects meet eligibility criteria.
11. For those that pass eligibility requirements and are females of childbearing potential, perform a urine pregnancy test. If the test is negative or candidate is male, the subject will be enrolled in the study.
12. Obtain close-range standard photography as described in section entitled, Assessments. This is standard of care.
13. Obtain photographs and measurements using the Vectra H2 3D Imaging System and VISIA and/or VISIA-CR as described in section entitled, "Assessment", for research purposes.
14. Study doctors will call in prescriptions to the subjects preferred pharmacy. This is standard of care.

This visit will take 30-45 minutes.

Visit 2, Visit 3, Visit 4: Treatment Visits 1-3

Day 0, Day 30, Day 60

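### Inclusion criterion 3 looks back to 1927nm laser in the past 3 months, while recruitment looks forward to laser still to be given; as written it refuses laser-naive candidates and allows a baseline in recently lasered skin

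*Combined protocol and SAP*

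**What the plan says.** Eligibility Criteria, inclusion criterion 3, under a heading that covers Part 1 and Part 2, reads: "Individuals undergoing fractionated 1927nm laser to treat hyperpigmentation in the past 3 months".

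Two other places describe who comes in:

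- Subject Enrollment: "Healthy subjects within the study population of interest who will be undergoing fractionated 1927nm laser to treat hyperpigmentation will be recruited".
- Pre-Study Procedures: people may be approached "if subjects express an interest in the procedure during a clinic appointment".

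Neither asks for an earlier laser session.

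The criteria are applied as a gate. Subject Enrollment states "Subjects meeting all eligibility requirements will be scheduled for an official screening visit", and Pre-Study Procedures says that "potential subjects will be screened for eligibility requirements via chart review on EPIC". Eligibility is checked again at the Screening visit in each Part.

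For Part 2, Subject Instructions makes Part 1 participants eligible if they complete the topical washout and refrain from other treatments. It does not mention criterion 3.

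**The concern.** The two texts admit different people. Someone who has never had 1927nm laser and is about to start fits the recruitment text and fails criterion 3. No section says which text prevails.

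The criterion reaches the primary endpoints. Both measure change from baseline, the study has no control group, and Statistical Methods of Analysis plans a paired comparison of baseline with later visits. Baseline is therefore the only comparator. If it is taken soon after a laser session, the change no longer starts from skin free of recent laser.

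The two possible harms are alternatives. If staff apply the criterion, baseline may be recently lasered. If they ignore it, each laser-naive enrolment is a departure from a written criterion, of the kind that the Data Monitoring section asks the Investigator to track.

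**Working it through.** The plan gives no figure to reproduce here. The check is a comparison of texts followed by day counts.

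**Texts side by side**

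| Candidate | Recruitment text | Criterion 3 as written |
|---|---|---|
| Never lasered, due to start | fits | fails |
| Last session more than 3 months ago, due more | fits | fails |
| Session within 3 months, due more | fits | fits |
| Session within 3 months, none planned | does not fit | fits |

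The texts agree only on the third row.

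**Inputs**

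- 3 months = 90 to 92 days (assumption).
- The look-back is counted to Screening (assumption; the documents name no visit).
- Part 1 Screening: Day -42 to -28.
- Last study laser: Day 60 ± 3, so Day 57 to 63.
- Follow-ups: Day 90 ± 7 and Day 150 ± 7 (schedule table).

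**Days since the last 1927nm laser**

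- Screening baseline under criterion 3: 0 to 90-92.
- Part 1 image before the first treatment: minimum 0 + 28 = 28; maximum 90 + 42 = 132, or 92 + 42 = 134.
- First follow-up: 83 − 63 = 20 to 97 − 57 = 40.
- Second follow-up: 143 − 63 = 80 to 157 − 57 = 100.

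On these assumptions the baseline range overlaps the post-laser period in which the outcomes are measured.

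If the 3 months were counted to Day 0 instead, a session before a Part 1 Screening visit would lie at most 92 − 28 = 64 days before that visit. On the criterion's wording alone, a qualifying session could even fall after the Screening image.

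The pre-treatment image range is given for Part 1 only. Part 2 Screening has two windows: "Visit 7 Day -30 to -1" in the schedule table and "Day -42 to -28 Days" in the visit text.

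**Part 1 continuers**

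- At Part 1 exit: 80 to 100 days post-laser by the schedule table. By the follow-up visit text (3 months ± 7 days after treatment, taken as 90 days after the last session) it is 90 − 7 = 83 to 90 + 7 = 97. Both ranges straddle 90-92.
- At Part 2 Day 0, with a 4-week washout starting at exit: at least 80 + 28 = 108, or 83 + 28 = 111. Both are beyond 92.

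So a continuer may pass or fail criterion 3 at exit, and fails it at Part 2 Day 0 on this washout assumption.

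**The case against.** The strongest reply is that the intent is fairly clear. Purpose and Objective, the study overview and the visit descriptions all concern laser to be given in the study. The criterion is ungrammatical and looks like a slip, and the two texts are not mutually exclusive. This is a single-site pilot of about 20 subjects and no stated figure is wrong. All of that stands, but none of it corrects a binding criterion.

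Other provisions give only partial cover. Exclusions 14, 17 and 25 depend largely on the Investigator's judgement. Exclusions 16 and 26 set 4-week intervals for microdermabrasion or glycolic acid and for hydroquinone and tretinoin, but no exclusion names prior laser. Inclusion criterion 4 covers aesthetic therapies only during the study.

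Four stronger readings are tempting and are not supported:

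- **That baseline will certainly be a Screening image within 3 months of laser.** The reference visit is not stated. Standard photography and the Skin Hyperpigmentation Index are tied to Screening, but the VISIA text says only baseline, and the treatment-visit text also lists VISIA imaging before the first treatment.
- **That the bias has a known direction or size.** The documents give nothing from which to derive either.
- **That continuers are barred from Part 2.** Subject Instructions can be read as a specific rule for them, although no text says that it overrides criterion 3.
- **That some continuers would still be within 3 months at Part 2 Day 0, because the schedule table's Part 2 Screening can be as late as Day -1.** The same schedule carries a 4-to-6-week washout line, and exclusion 26 also requires 4 weeks. The inference would need washout to begin before Part 1 exit. One instruction, listing 4 weeks of post-treatment topicals, might allow that; another continues them to the end of the study. That is a separate scheduling question.

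**Conclusion.** The inconsistency is real and criterion 3 is wrong as written, even if by a slip. It refuses laser-naive candidates whom the recruitment text invites, and it allows the sole comparator to be taken in recently lasered skin. Counted to Screening, with 3 months as 90-92 days, the gap is 0 to about 90-92 days at a Screening baseline and about 28 to 134 days at a Part 1 image before the first treatment. The status of Part 1 continuers is unclear as well.

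The conclusion rests on two texts that define different populations under a binding entry rule, with nothing to reconcile them. It does not rest on a sized bias. It should be corrected by amendment.

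**What to change.** Reconcile criterion 3 with Subject Enrollment, Pre-Study Procedures and the Part 2 Subject Instructions. Amend it to one rule on prior 1927nm laser, chosen by the sponsor, that states:

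- the period it covers;
- the visit to which that period is counted;
- whether it applies to subjects continuing from Part 1.

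Record the date of any prior 1927nm laser in the medical history already taken at Screening, whose listed items do not name it. If the chosen rule admits people with and without recent laser, a descriptive report of change from baseline by prior-laser status is optional; with about 20 subjects the groups would be small.

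Cost: a short amendment and one data field.

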The primary objective of this study is to quantify the hyperpigmentation response after 1927nm non-ablative fractionated laser therapy in subjects with Fitzpatrick Skin Phototypes V and VI and explore an effective, adjunctive pre- and post-procedural topical regimen to prevent iatrogenic dyspigmentation or scarring in this population.

We will explore this question with a non-blinded, observational study at a single center.

Clinical Study Design

Overview of Clinical Study

This is a single-site, prospective observational, non-randomized, non-controlled pilot study being conducted at the University of Texas Southwestern Medical Center at Dallas in the Department of Plastic Surgery. The study is designed to follow changes in hyperpigmentation in approximately 20 qualified and consenting subjects receiving f1927 hyperpigmentation standard care treatment using VISIA and/or VISIA-CR. The Principal Investigators (PIs) have been selected based on their expertise, qualifications, subject access, prior clinical research, facilities, and interest in this field of research. Subjects will be recruited through IRB-approved advertisements or identified by [name] at the University of Texas Southwestern Medical Center. Subjects will be numbered sequentially in the order in which they initially qualify for entry into the study. Subjects who continue the study from Part 1 will retain their subject number through Part 2. Any new subjects recruited for Part 2 will be numbered sequentially in the order they qualify for entry into the study.

Part 1:

Study doctors will explain and prescribe subjects a standard of care topical regimen 4-6 weeks prior to f1927 treatments.

Part 2:

Subjects will be asked to complete a month-long washout period of all topical regimens prior to f1927 treatments. Following each treatment subjects will be asked to apply Clobetasol twice a day for four days and apply ice to the treated areas four times a day.

Clinical Treatment and Assessments

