Following the final treatment, patients should continue to take their 4% Hydroquinone and Tretinoin 0.1% cream as prescribed through the remainder of the study.

Part 2:

Subjects will be asked to refrain from using any topical prescription medications on their face for at least 4 weeks prior to treatments commencing. Subjects who participated in Part 1 will be eligible for Part 2 if they agree to complete the topical regimen washout period and agree to refrain from any other treatments for the remainder of their trial participation.

Pre-Treatment Instructions:

Subjects will be asked to wash off all skincare products at least 30 minutes prior to each scheduled clinic visit using a cleanser of your choice. If a subject arrives having not removed skincare products, she or he will be required to remove the residual product at the clinic and wait at least 20 minutes prior to procedures.

Post-treatment Instructions:

Immediately post-treatment Clobetasol Propionate 0.05% and ice will be applied to the treated areas for 15-20 minutes. The subject will be instructed to re-apply Clobetasol Propionate 0.05% twice a day and ice the treated area for 15 minutes up to four times a day for four days.

Blistering, bleeding, oozing, strong pain, swelling persisting for more than 24 hours, or signs of infection (e.g., pus, drainage, fever) are cause for immediate concern and you should contact the investigator and/or his designee to be evaluated and potentially treated at no cost to the subject.

Subjects will be asked to avoid extended periods of sun exposure and all use of tanning beds for the duration of the study. Extra care should be taken to wear protective clothing and avoid sun exposure from 10 AM to 4 PM.

Subjects will be encouraged to consistently use face wash, moisturizer, and sunscreen of their choosing. Subjects will be asked to refrain from using any new anti-aging, acne, and acne scar products or devices and beginning the use of any new skincare products or devices other than the assigned test material for the duration of the study.

Study Design

Study Timeline and Procedures

Study Procedure		Part 1						Part 2					
		Screening	Treatments			Follow Up		Screening	Treatments			Follow Up	

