The procedure will then be performed in our Plastic Surgery clinic following standard of care procedures. A trained staff member will apply a topical triple anesthetic (benzocaine, lidocaine, tetracaine) to anesthetize the areas being treated. After allowing 10 minutes for the anesthetic to take effect, the skin will be cleansed and prepped with antiseptic. A trained staff member will treat the subject's face with f1927. Treatment settings and parameters will be determined by the provider and will be chosen according to Fitzpatrick skin type and location of the body for which it will be used. Ultimately, 4-6 passes will be performed at the discretion of the treating provider. Post-treatment cooling will be offered at the discretion of the treating provider, depending on clinical need.

Appropriate post-treatment care instructions will be provided as deemed appropriate by the Investigator or study staff. Post-treatment assessment will be performed. Subjects will be instructed that blistering, bleeding, oozing, strong pain, swelling persisting for more than 72 hours, or signs of infection (e.g., pus, drainage, fever) are cause for immediate concern and they should contact the investigator and/or his designee, to be evaluated. Expected downtime is minimal after treatment, typically lasting 0-3 days.

These visits will take approximately 1 hour.

Visit 5 and Visit 6: Follow-Up Visits 1 and 2

Day 90, Day 150

At a minimum, all subjects will return for follow-up visits at 1 month (\pm 7 days) and 3 months (\pm 7 days) after treatment.

The following activities will be performed on all study subjects during the follow-up visits:

1. The physician or study staff will ask subjects if they have experienced any changes in their health since the previous visit. Changes will be recorded accordingly. If an adverse event (AE) is reported than the Investigator will be informed, and an AE form will be completed. This is standard of care.
2. Subjects will acclimate to ambient temperature and humidity conditions for 15 minutes prior to any procedures being done. This is standard of care.
3. The physician or study staff will perform an examination of the skin in the treatment area. This is standard of care.
4. Obtain post-treatment close-range clinical photography as described in section entitled, "Assessments", for research purposes.

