Appropriate post-treatment care instructions will be provided as deemed appropriate by the Investigator or study staff. Post-treatment assessment will be performed. Subjects will be instructed that blistering, bleeding, oozing, strong pain, swelling persisting for more than 72 hours, or signs of infection (e.g., pus, drainage, fever) are cause for immediate concern and they should contact the investigator and/or his designee, to be evaluated. Expected downtime is minimal after treatment, typically lasting 0-3 days.

These visits will take approximately 1 hour.

Visit 4 and Visit 5: Follow-Up Visits 1 and 2

Day 90, Day 150

At a minimum, all subjects will return for follow-up visits at 1 month (\pm 7 days) and 3 months (\pm 7 days) after treatment.

The following activities will be performed on all study subjects during the follow-up visits:

7. The physician or study staff will ask subjects if they have experienced any changes in their health since the previous visit. Changes will be recorded accordingly. If an adverse event (AE) is reported than the Investigator will be informed, and an AE form will be completed. This is standard of care.
8. Subjects will acclimate to ambient temperature and humidity conditions for 15 minutes prior to any procedures being done. This is standard of care.
9. The physician or study staff will perform an examination of the skin in the treatment area. This is standard of care.
10. Obtain post-treatment close-range clinical photography as described in section entitled, "Assessments", for research purposes.
11. Obtain post-treatment photographs using the Vectra H2 3D Imaging System, as described in section entitled, "Assessments", for research purposes
12. Obtain post-treatment photographs VISIA and/or VISIA-CR as described in section entitled, "Assessments", for research purposes.

These visits will take about 30 minutes.

Assessments

Photography Procedures

Nikon D7200 (Standard of Care)

Standard and close-range of the face will be utilized for evaluation of pigmentation. These photographs will be taken utilizing the Nikon D7200 at Baseline (Screening Visit), 1-month post-treatment and 3-months post-treatment.

Vectra H2 3D Imaging System (Standard of Care)

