A mild bruising may occur at the treatment area. This is usually transient and resolves in a few hours to few days.

Transient edema and/or erythema (Common)

Edema and erythema typically develop within the irradiated areas but are usually temporary and fade within 24-72 hours. There is a 90% chance of transient edema and 99% chance of erythema to occur after treatment.

Skin roughness and/or peeling (Common)

Patients can expect their treated skin to feel rough like sandpaper for a few days while the skin heals. This is transient and should resolve in a few days. This is specific to the f1927 treatment.

Pigmentary changes (Rare)

This treatment can cause undesired pigmentary changes such as hyper or hypopigmentation. Although this is usually temporary, it may be permanent on rare occasions. Sun avoidance and/or the use of total sun block (SPF 30 or higher) will help to minimize the intensity and duration of pigmentary changes.

Eye injury (Rare)

There is a risk of eye injury associated with the use of this device. This risk will be minimized by wearing protective eyewear designated for use with this device. All subjects and other personnel must use proper protective eyewear during the use of this device

Scarring (Rare)

There is a small risk of scarring. However, this is minimized by proper technique and wound care.

Post-Treatment: Clobetasol (Rare)

Clobetasol is a corticosteroid that helps reduce inflammation, redness and itching on the body. Side effects of topical Clobetasol are rare and include burning, itching, swelling, irritation, dry skin, redness, rash, acne or temporary hair loss.

Standard of Care Risks and Research Risks

Assessment: Photography

Photographs will be taken using standard close-range photography, standard 3D photography using the Vectra H2, and the VISIA and/or VISIA-CR. The subject may be uncomfortable with sitting still for an extended period of time or from turning his/her body in various positions. Subjects may be sensitive to bright and repeating flashes from the camera, which can sometimes cause headaches, eye irritation, discomfort, aftereffects such as seeing spots, and in rare cases, could stimulate a migraine headache or epileptic seizure.

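### Part 2 subjects are told to contact the investigator about swelling after 24 hours in one section and after 72 hours in another

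*Combined protocol and SAP*

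**What the plan says.** The warning about swelling appears three times in the combined protocol and SAP, and a fourth section describes the expected course.

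- **Subject Instructions, Part 2, Post-treatment Instructions.** The trigger is "swelling persisting for more than 24 hours". This and the other listed signs "are cause for immediate concern and you should contact the investigator and/or his designee to be evaluated and potentially treated".
- **Part 2, Treatment Visits 1-3 (Day 0, Day 30, Day 60).** The trigger is "swelling persisting for more than 72 hours". The listed signs "are cause for immediate concern and they should contact the investigator and/or his designee, to be evaluated".
- **Part 1, Treatment Visits 1-3.** The wording and the 72-hour trigger are the same as in the Part 2 visit text.
- **Potential Risks, Transient edema and/or erythema (Common).** These reactions "are usually temporary and fade within 24-72 hours". The section adds: "There is a 90% chance of transient edema and 99% chance of erythema to occur after treatment".

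**The concern.** A Part 2 subject leaves each laser session under both Part 2 texts. If swelling is still present on the second or third day, the Post-treatment Instructions call for prompt contact with the investigator and the treatment-visit text does not. Study staff who give the advice cannot follow both.

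The first thing at stake is a safety instruction to the subject. The second is a limited effect on safety data. Secondary endpoint 1 covers the incidence, severity and relatedness of adverse events. Under Data Monitoring, events between visits reach the site when the subject makes contact, and an unscheduled visit can then be arranged for evaluation and photographs. The trigger a subject has been given may therefore affect whether swelling is seen while it is there or only described later.

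**Working it through.** The document contains no calculation on this point, so the check is a comparison of texts with one subtraction.

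**1. Do the two Part 2 texts cover the same event?** Yes. Both sections give the same clobetasol and ice instruction for the time immediately after treatment and the four days that follow. They describe aftercare for the same subjects after the same session.

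**2. Do they differ in anything except the duration?**

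| Element | Post-treatment Instructions (Part 2) | Treatment Visits 1-3 (Part 2) |
|---|---|---|
| Other warning signs (skin signs, pain, infection) | Listed | Same list |
| Swelling trigger | More than 24 hours | More than 72 hours |
| Urgency | Immediate concern | Immediate concern |
| Action | Contact investigator or designee for evaluation | Contact investigator or designee for evaluation |

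The Post-treatment Instructions also mention possible treatment at no cost to the subject. That does not change when contact should be made. The swelling trigger is the only element on which a subject would act differently.

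**3. How wide is the disagreement?** 72 − 24 = 48 hours, that is, the second and third days after the session. At or before 24 hours neither text calls for contact on account of swelling. Beyond 72 hours both do.

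**4. Where does that window fall?** Potential Risks gives 24-72 hours as the usual time for edema and erythema to fade, the same two limits, and states a 90% chance of edema. The conflict therefore concerns the expected course of a common reaction and not a rare late event.

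**5. Does another section settle it?** I found no order of precedence and no reason for the difference. All of these sections are current operative text, and nothing is redacted at these points.

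**6. Where does the Part 1 text stand?** It applies to Part 1 sessions, while the 24-hour warning sits under Part 2. It does not by itself give a Part 2 subject conflicting advice. A subject who takes part in both Parts would meet both texts. If the 24-hour paragraph were read as covering both Parts, the Part 1 text would conflict with it as well.

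**7. When would the site otherwise learn of the swelling?** At the next scheduled visit, which is about 30 days after each session (Days 0, 30, 60 and 90 in the Study Timeline and Procedures). Swelling that lasts one to three days would by then be recalled and not observed.

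**The case against.** The strongest reply is that neither duration defines an adverse event. Each only tells the subject when to call. Capture is set out elsewhere and does not depend on how long swelling lasts. Under Adverse Events, an open-ended question is asked at each visit. The treatment and follow-up visits include a question about changes in health. Data Monitoring asks subjects to make contact if adverse events develop between visits. This stands. A reader might infer that swelling of 24 to 72 hours is recorded as an adverse event under one text and lost under the other, but the document does not support that. What remains is narrower: the timing of calls, and whether swelling is examined while present, may vary.

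A reader might also infer that subjects receive differing handouts. The document describes no instruction sheet, and the visit texts leave post-treatment care instructions to the investigator or staff. What subjects are actually told is not known. The contradiction lies in the protocol.

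A reader might also try to size the problem as 0.90 × 20 × 3 = 54 sessions with edema in a Part. This is not a usable estimate. It takes "approximately 20 qualified and consenting subjects", which is the study total, as the enrolment of one Part. It applies the 90% to each session, which the document does not say. As a count of conflicting advice, it would also need every episode to last beyond 24 hours. The lower end is 0, so the range carries no information.

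Finally, the expected course in Potential Risks might be read as showing which duration is right. It does not: it describes what usually happens, not when a subject should be examined. That choice is clinical.

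**Conclusion.** The plan is wrong as written. For the same Part 2 subject after the same session, two operative sections attach the same urgent action to swelling durations 48 hours apart, and nothing in the document resolves the conflict. It matters because the disputed window is the one in which a reaction given a 90% chance is expected to fade.

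The effect on data is possible and limited. Calls between visits and examination of swelling while present may differ according to the text followed. Elicitation of adverse events at visits is the same under either text, and the primary pigmentation endpoints are untouched. The number of subjects affected cannot be derived from the document.

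The conclusion assumes that the 24-hour paragraph applies to Part 2, where it is placed, and that swelling in the instructions is the same reaction as edema in Potential Risks. The contradiction itself does not depend on the second assumption; the link to the 90% figure and the 24-72 hour course does.

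**What to change.** Reconcile the Post-treatment Instructions under Subject Instructions, Part 2, with the Part 2 text for Treatment Visits 1-3, and align the Part 1 text for Treatment Visits 1-3. One swelling-contact instruction, chosen by the sponsor on clinical grounds, should appear in the same words wherever the warning is given. If a difference between the Parts is intended, the protocol should say so and give the reason. This review takes no position on which duration is right.

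The cost is a wording amendment. It needs no new visit, procedure or data item, and no change to the analysis.
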